## **7.8.2 Laboratory data**

The analysis of laboratory data will be descriptively in nature and will follow standard procedures. The analysis of laboratory data will use the same “analyzing treatments” as described for AEs, except for that the baseline laboratory values will be included in the “on treatment” period. Patients having at least one post-baseline laboratory value will be displayed in the descriptive analyses. Patients with missing CTCAE grade at baseline or no baseline value but with post-baseline value will be displayed in the category “Missing CTCAE grade at baseline”.

Descriptive statistics, including change from baseline, frequency of patients with transitions relative to the references range, will be provided for laboratory assessments at scheduled visits. Data collected during potential unscheduled laboratory assessments will be listed. No post-study laboratory values will be considered. CTCAE grade for applicable laboratory parameters will be calculated according to CTCAE v5.0. The following outputs will be presented:

- Baseline, last value and difference from baseline
- Worst CTCAE grade experienced during the on-treatment period
- Transitions of the CTCAE grade from baseline to the worst lab values, from baseline to the last lab values, and from the worst to last values during the on-treatment period
- Possible clinically significant laboratory values
- Transitions for laboratory values without CTCAE grade based on reference ranges

Note: For calculating the change in CTCAE grade from baseline, patients with a CTCAE grade of -9 (no CTCAE grade defined) or CTCAE grade of -5 (overlapping reference ranges) will be treated as a CTCAE grade 0 for all analyses. In laboratory listings, the CTCAE grade is displayed as -9 and -5, respectively.

For Uric Acid, Hypokalemia, amylase, bicarbonate, eosinophils, glucose (high direction), INR of prothrombin time, lipase, methemoglobin, sodium (low direction) the CTCAE grade cannot always be assigned by the laboratory parameter itself as two different CTCAE grades have the same laboratory constellation, but are distinguished by additional clinical parameter. In this case a CTCAE grade of -1 will be assigned. These will not be considered for laboratory analyses. In laboratory listings, the CTCAE grade is displayed as -1, respectively.

Patients with hepatic enzyme elevation will be tabulated.

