**Table 6.1: 1 Dose levels for escalation in Schedule A**

Cohort Dose Level	Proposed dose	Increment from previous dose
1	1.0 mg/kg/q3w	Starting dose
2	2.5 mg/kg/q3w	150%
3	5.0 mg/kg/q3w	100%
4	7.0 mg/kg/q3w	40%
5	8.5 mg/kg/q3w	21.4%

The data will be presented for all dose cohorts separately and in total over all dose cohorts. DLTs occurring during the MTD evaluation period (during the first treatment cycle) will be presented separately.

“Analysing treatment” will be used for reporting of treatment-emergent adverse events (AEs) and to differentiate between screening, on-treatment, and post-treatment safety data. The inequalities start date $\leq$ onset date of the AE $<$  end date of the AE will determine whether the AE will be assigned to the “analysing treatment” or not.

The treatment periods of the trial which will be used for the reporting of AEs and safety laboratory parameters are given in [Table 6.1: 2](#). Safety data recorded during the Residual Effect Period (REP) will be considered as on-treatment. In this trial, the REP is defined as 42 days.

If not specified otherwise, all safety tables will be based on the on-treatment period. AEs that have an onset date during the screening or post-treatment periods will be displayed in separate listings.

**Table 6.1: 2** Definition of treatment periods

Analysing Treatment Period	Start Date (including)	Stop Date (excluding)
Screening	Date of informed consent	The date of first trial medication administration
On-treatment	Date of first administration of trial medication	Date of last trial medication administration + REP*, or death, +1 day whichever comes first, e.g., actual on-treatment period + REP*,
Post-treatment	Last day of on-treatment period +1 day	Date of the last contact date or death, or DBL date, whichever comes first +1 day
MTD evaluation period	Date of first administration of trial medication	Date of first administration of trial medication +21 days

\*Note: A 42-day residual effect period (REP) is defined.

The initial dose of trial medication assigned at the beginning of the first treatment cycle will be used as the label of the analysing treatment.

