### **Baseline definition**

Unless otherwise specified, baseline is defined as the time point closest to and prior to the first administration of study treatment. Note that for some study procedures (e.g. body weight, vital signs, laboratory tests) baseline may be the measurement made on the same day the study treatment was started. In such cases these measurements will be assumed to have been taken according to the protocol, i.e. prior to the first administration of study treatment. But for some measurements, the examination time may also need to be considered, in instances where

time is recorded in addition to date. If not available, then the values reported at the screening visit will be considered.

For laboratory parameters for which not only the examination date but also the sampling time was recorded, examination time should be taken into consideration when defining baseline. That is a laboratory measurement on the same date as the first administration of study treatment is considered as baseline if and only if the examination time of this laboratory measurement is before the first administration of study treatment.

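### SAP 7.8.2 takes the worst on-treatment laboratory grade over a period that includes baseline, so it cannot fall below the pre-dose grade

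*SAP*

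**What the plan says.** SAP 6.1 sets the periods in Table 6.1: 2 for adverse events and safety laboratory parameters alike. There the on-treatment period starts on the date of first administration, and earlier data belong to screening. SAP 6.7 makes baseline a pre-dose value: "baseline is defined as the time point closest to and prior to the first administration of study treatment".

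SAP 7.8.2 then departs from that table for laboratory data. It uses the adverse event periods with one exception: "the baseline laboratory values will be included in the" on-treatment period. Among the planned outputs are:

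- a summary by grade, listed as "Worst CTCAE grade experienced during the on-treatment period";
- shift tables, the first of which is given as "Transitions of the CTCAE grade from baseline to the worst lab values". Two further shifts compare baseline with the last value and the worst value with the last.

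The section's rule on which patients to show is "Patients having at least one post-baseline laboratory value will be displayed in the descriptive analyses". SAP 6.1 presents the data by dose cohort and in total.

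**The concern.** A table of the worst on-treatment grade is normally read as what happened after dosing. Once a pre-dose value joins the set over which the worst is taken, an abnormality that existed only before the first infusion appears under the on-treatment label.

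This is also out of line with the SAP's own approach to adverse events. Under SAP 7.8.1, an event that began before first dosing counts as treatment-emergent only if it deteriorates. Under SAP 7.8.2, a pre-dose laboratory grade enters the on-treatment worst even if it improves.

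The situation can arise in this population. Protocol 3.3.2 admits AST and ALT up to 3 x ULN (5 x ULN with liver metastases), ALP below 5 x ULN, and bilirubin and creatinine above ULN within limits. There is no control arm against which a reader could discount carried-over abnormalities. At stake is the accuracy of the descriptive laboratory safety tables at each dose.

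**Working it through.** The plan gives no figure to reproduce. The check is on the rule itself, followed by an illustration of size under stated assumptions.

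**1. Does anything remove baseline from the worst value?** No.
- The post-baseline condition in SAP 7.8.2 decides which patients are displayed, not which of their values count.
- Grades coded -9 or -5 are treated as 0 and grades of -1 are left out. Neither convention separates pre-dose from post-dose values.
- A missing baseline is filled from screening (SAP 6.6), which is still pre-dose.

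**2. Consequence.** Let b be the baseline grade and p1, ..., pk the post-baseline grades.
- As written: W = max(b, p1, ..., pk), so W ≥ b always.
- Post-baseline only: W* = max(p1, ..., pk).
- W exceeds W* only when every p is below b. In all other patients the two agree.

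**3. Enumeration.** Take grades 0 to 4 at baseline and at three later visits, which gives 5 x 5 x 5 x 5 = 625 patterns.
- As written, worst below baseline: 0 of 625.
- Post-baseline only: b³ patterns for each baseline grade b, so 0 + 1 + 8 + 27 + 64 = 100 of 625.
- Cells of the 5 x 5 baseline-to-worst table that can be filled: 5 + 4 + 3 + 2 + 1 = 15 as written, against 25 with post-baseline values only. The 10 improvement cells are empty by construction.

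These counts give every pattern equal weight. They confirm the logic and say nothing about how often it occurs.

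**4. One pattern followed through the tables.** Baseline grade 2, later grades 1, 0, 1:

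| Output | As written | Post-baseline only |
|---|---|---|
| Worst on-treatment | 2 | 1 |
| Baseline to worst | 2 to 2 | 2 to 1 |
| Worst to last | 2 to 1 | 1 to 1 |
| Baseline to last | 2 to 1 | 2 to 1 |

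The first three rows change. The last does not.

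**5. Size under assumed rates.** None of these rates is in the documents. Let q be the share at grade ≥2 at baseline (10-30%), r the share of those below grade 2 at every later visit (25-50%), and e new onset among the rest (5%).
- Share with worst grade ≥2 as written: q + (1 - q)e.
- Post-baseline only: q(1 - r) + (1 - q)e.
- Excess: the difference, q x r. It does not depend on e.

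| q | r | As written | Post-baseline only | Excess (points) |
|---|---|---|---|---|
| 10% | 25% | 14.5% | 12.0% | 2.5 |
| 10% | 50% | 14.5% | 9.5% | 5.0 |
| 20% | 25% | 24.0% | 19.0% | 5.0 |
| 20% | 50% | 24.0% | 14.0% | 10.0 |
| 30% | 25% | 33.5% | 26.0% | 7.5 |
| 30% | 50% | 33.5% | 18.5% | 15.0 |

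The excess therefore runs from 2.5 to 15 points. Subtracting the ends of the two overall ranges (14.5 - 9.5 and 33.5 - 26.0) gives 5 to 7.5 points, but those ends belong to different recovery rates and do not bound the excess.

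**6. By cohort.** Protocol 3.1 allows cohorts with a minimum of 2 or 3 patients. In a cohort of that size, one such patient moves a row by 1/2 or 1/3.

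**The case against.** The strongest reply is that the sentence only labels data. Table 6.1: 2 assigns periods by date. A baseline drawn pre-dose on Day 1 falls on the first on-treatment date, while one taken up to 3 calendar days earlier, as the Schedule A flow chart permits, falls in screening. Placing every baseline in one period makes change from baseline simple to compute. SAP 7.8.2 also treats baseline and worst as separate quantities in its transition tables and refers to standard procedures that are not reproduced. This reading is plausible, but the SAP does not state it, and the literal rule gives a different table.

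Other parts of the reply stand and limit the point:

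- A reader might infer that improvement disappears from the laboratory tables. It does not. Baseline-to-last transitions and differences from baseline still show it, and the transition tables disclose the baseline grade.
- A reader might infer that the rule adds every abnormal baseline to the on-treatment count. It does not. A patient whose abnormality persists is counted with or without baseline in the set. Eligibility limits show that abnormal values are allowed, not how common they are.
- A reader might infer that dose decisions were affected. The documents do not support this. Under Protocol 3.1 and 4.1.3, escalation rested on DLTs, Grade ≥2 toxicity, PK and the BLRM. SAP 4 says the trial ends early without determining an MTD or OBD.

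**Conclusion.** The point stands as a fault in a descriptive derivation. As written, SAP 7.8.2 gives a worst on-treatment grade that is the larger of the baseline and post-baseline grades. This biases the stand-alone worst-grade table upward, empties the improvement side of the baseline-to-worst table, and lets the worst-to-last table show a pre-dose abnormality as an on-treatment one that recovered.

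The excess equals the share of patients who are better than baseline at every later visit. For the grade ≥2 share it is 2.5 to 15 percentage points under the assumed rates above. The true figure depends on data that the documents do not give. That the rule permits the error is certain from the text; how far it distorts the tables is not known.

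No hypothesis test, DLT count, MTD analysis or adverse event table depends on it. It should be corrected because the tables would otherwise say something that their label does not mean, and because correction costs almost nothing.

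**What to change.** Add one sentence to SAP 7.8.2: the worst on-treatment grade, wherever it is used, is derived only from values obtained after the first administration, and baseline serves solely as the reference for change and transitions. Values from the day of first dosing should be classed as pre-dose or post-dose by the timing rule already in SAP 6.7, because a date filter alone would let a pre-dose Day 1 sample back in.

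No change is needed for the last value, since displayed patients already have a post-baseline value. If the sponsor meant the inclusion of baseline only as a labelling step, the same sentence records that.

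The cost is the sentence and one programming filter. No new data are needed and no other analysis changes.

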5.2.3 Safety laboratory parameters

Safety laboratory parameters will be analysed at a local laboratory. Safety laboratory examinations will include tests as listed in [Table 5.2.3:1](#), and should be obtained at the time points specified in the [Flow Chart](#).

Table 5.2.3:1 Safety Laboratory Tests

Category	Parameters
Haematology	Red blood cell count (RBC), haemoglobin, haematocrit, platelet count, reticulocytes, white blood cell count (WBC) with differential (neutrophils, bands, lymphocytes, monocytes, eosinophils, basophils)
Coagulation	International Normalized Ratio (INR), activated Partial Thromboplastin Time (aPTT)
Biochemistry	Glucose, sodium, potassium, calcium, phosphate, magnesium, chloride, bicarbonate (HCO ₃), urea, creatinine, AST, ALT, alkaline phosphatase, lactate dehydrogenase (LDH), bilirubin, total protein, albumin. Creatinine clearance, creatine phosphokinase, cholesterol and triglycerides if indicated.
Immunoglobulins	Serum immunoglobulin levels (IgG, IgM, IgA, IgE) and direct antiglobulin test to be measured at Screening and repeated if an infusion related reaction occurs.
Urinalysis	pH, protein, glucose, blood, leucocytes, nitrite; in case of pathological finding further evaluation should be performed and results documented
Pregnancy test	β-HCG testing in urine or serum in women of childbearing potential (WOCBP)

In case of haematological toxicity of Grade 4, or other haematological AEs fulfilling the criteria for DLT, a complete blood count has to be performed at least twice per week until improvement to a lower grade. The investigator should complete additional evaluations of laboratory tests as clinically indicated. Any abnormal and clinically relevant findings from these investigations need to be reported as an AE.

In case the criteria for possible hepatic injury are fulfilled, a number of additional tests will be performed (please see [Section 5.2.6.1](#) and the “DILI Checklist” provided in the study portal and the ISF).

In addition to the tests above, a blood test for Vitamin D (25-hydroxy vitamin D) will be performed at Screening, every third cycle (Cycle 3 Day 1, Cycle 6 Day 1, etc.) and at EOT. This will be analysed at a local laboratory.

5.2.4 **Electrocardiogram**

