7.3.4 Safety analyses

Adverse events will be coded using the Medical Dictionary for Drug Regulatory Activities (MedDRA). Standard BI summary tables and listings will be produced. All adverse events with an onset between start of treatment and end of the residual effect period (REP), a period of 42 days after the last dose of trial medication, will be assigned to the on-treatment period for evaluation.

All treated patients will be included in the safety analysis. In general, safety analyses will be descriptive in nature and will be based on BI standards. No hypothesis testing is planned.

Statistical analysis and reporting of adverse events will concentrate on treatment-emergent adverse events, i.e. all adverse events occurring between start of treatment and end of the residual effect period. Adverse events that start before first drug intake and deteriorate under treatment will also be considered as 'treatment-emergent.'

Frequency, severity, and causal relationship of adverse events will be tabulated by system organ class and preferred term after coding according to the current version of MedDRA at the database lock.

Laboratory data will be analysed both quantitatively as well as qualitatively. The latter will be done via comparison of laboratory data to their reference ranges. Values outside the reference range as well as values defined as clinically relevant will be summarised. Treatment groups will be compared descriptively with regard to distribution parameters as well as with regard to frequency and percentage of patients with abnormal values or clinically relevant abnormal values.

Vital signs, physical examinations, or other safety-relevant data observed at Screening, baseline, during the course of the trial and at the end-of-trial evaluation will be assessed with regard to possible changes compared to findings before start of treatment.

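### SAP 7.8.2 excludes laboratory values that fit two CTCAE grades without a fallback, so worst-grade tables can understate toxicity or lose a patient

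*SAP*

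**What the plan says.** SAP 7.8.2 (Laboratory data) names uric acid, hypokalaemia, amylase, bicarbonate, eosinophils, high glucose, INR, lipase, methaemoglobin and low sodium. For these, it notes that sometimes "two different CTCAE grades have the same laboratory constellation, but are distinguished by additional clinical parameter". The rule then has three parts:

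- Coding: "In this case a CTCAE grade of -1 will be assigned".
- Analysis: "These will not be considered for laboratory analyses".
- Display: "In laboratory listings, the CTCAE grade is displayed as -1, respectively".

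The same section plans outputs that depend on the grade, among them "Worst CTCAE grade experienced during the on-treatment period" and "Transitions of the CTCAE grade from baseline to the worst lab values", together with transitions from baseline to last and from worst to last value. It also plans outputs that need no grade: baseline, last value and difference, and transitions relative to the reference range.

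Other ungradable results are treated differently. Codes -9 and -5 count as grade 0, and a patient with a missing baseline grade has a category of their own. Only -1 is left out with nothing in its place.

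Protocol 7.3.4 (Safety analyses) makes a broader commitment: "Values outside the reference range as well as values defined as clinically relevant will be summarised".

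**The concern.** A result coded -1 is not uninformative. It is one of two known grades, so it already establishes at least the lower one. What is unknown is only whether the higher one applies. Excluding it discards the part that is known.

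This matters most for a maximum. The worst grade is taken over the values that remain, so if the excluded value was the worst, a milder value from another visit takes its place. If no other value can be graded, the patient has no entry for that parameter. These tables are shown by dose cohort, and the protocol's minimum cohort is 2 or 3 patients, so a single shifted patient would be visible.

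**Working it through.** The plan states no figure for this rule, so there is none to reproduce. The check concerns direction, reach and possible size.

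**1. Direction in the worst-grade table.** For one patient and one parameter, let T be the true worst grade and K the maximum over the values that are kept. The kept values are a subset of all values, so K ≤ T whenever K exists. Example: grade 0, then an ambiguous 2/3, then grade 1. The true worst is 2 or 3 and the table shows 1.

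An enumeration confirms this. Each of three visits is either an unambiguous grade 0 to 4 (5 states) or one of four assumed ambiguous pairs, 1/2, 1/3, 2/3 or 3/4, with either grade true (8 states). That gives 13³ = 2,197 patterns:

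| Result of excluding -1 values | Patterns |
|---|---|
| Worst grade raised | 0 |
| Worst grade lowered | 720 |
| No gradable value left (8³) | 512 |
| Worst grade unchanged (2,197 - 720 - 512) | 965 |

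The pairs are assumptions, because the SAP does not list them. The counts show direction only and are not expected frequencies.

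**2. Direction in the transition tables.** Here the effect is not one-way.

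- Baseline to worst: if the dropped value was the worst, worsening is understated.
- Last value: an unambiguous grade 3 followed by an ambiguous 1/2 at the last visit. Dropping the last value leaves grade 3 as the last grade, and the improvement is hidden.
- Baseline: an ambiguous Day 1 value is dropped. If a grade 0 screening value stands in (SAP 6.6 and 6.7 allow screening values to serve as baseline), worsening is overstated. If nothing stands in, the patient may fall in the missing-baseline category.

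**3. Reach.** Protocol 5.2.3 lists the scheduled tests. The biochemistry row begins "Glucose, sodium, potassium, calcium, phosphate, magnesium, chloride, bicarbonate", which covers four of the ten parameters. INR is in the coagulation row and eosinophils are in the haematology differential. That makes six. Uric acid, amylase, lipase and methaemoglobin are not in the scheduled panel.

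**4. Possible size, on assumed inputs.** The documents do not say how many values will be coded -1. As an illustration only, take n = 30 (the planned number per schedule; the SAP reports early termination, so the actual number may differ) and one parameter. Let a be the share of patients whose worst value is abnormal, and q the share of those whose worst value is ambiguous while all their other values are normal.

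- Patients truly abnormal = n·a. Expected number tabulated as abnormal = n·a·(1 - q).
- Chance that at least one patient is understated = 1 - (1 - a·q)^n.

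| a | q | Truly abnormal | Tabulated | Chance of at least one understated |
|---|---|---|---|---|
| 0.1 | 0.1 | 3 | 2.7 | 26% |
| 0.1 | 1.0 | 3 | 0 | 96% |
| 0.5 | 0.1 | 15 | 13.5 | 79% |
| 0.5 | 1.0 | 15 | 0 | about 100% |

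The range is wide because a and q are unknown.

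One patient is 1/2 = 50, 1/3 = 33 or 1/6 = 17 percentage points in a cohort of 2, 3 or 6. The sizes 2 and 3 are the minimums in Protocol 3.1, and 6 comes from one of the MTD criteria in Protocol 7.1. Actual cohort sizes are not given. These figures describe how coarse the tables are, not the effect of the rule.

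**5. The alternative.** Let L be the maximum when each -1 value is counted at its lower candidate grade. No value is counted above its true grade, and none of the kept values is removed, so K ≤ L ≤ T. L also exists for a patient whose values are all -1. In the worst-grade table it is therefore never further from the truth than the current rule.

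**The case against.** The case for leaving the rule alone has real content.

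- **The safety information has another route.** Protocol 5.2.6.1 has laboratory changes that the investigator judges clinically relevant recorded as adverse events. SAP 7.8.1 tabulates these by dose and highest grade. That route can use the clinical information that separates the two grades. The values also remain in the listings. This stands and limits the harm, but it does not correct the laboratory tables.
- **The sentence may be narrower than it looks.** A reader might infer that the measured values are removed from every laboratory output. The sentence follows directly on the assignment of the grade, so it can refer to the grade alone, and several outputs need no grade. The text exempts nothing, so either reading is open. The point holds on the narrow one.
- **The SAP states its convention openly, and the tables are descriptive.** That is true. But following the convention as written gives a lower worst grade whenever the excluded value was the worst, so the issue is more than missing detail.
- **The lower grade can still be too low.** That is also true. It is closer than exclusion in the worst-grade table, and a footnote can show the remaining uncertainty.

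**Conclusion.** The point stands as a cheap improvement. In the worst-grade table, a -1 value that is the patient's worst leads to a grade that is too low or to loss of the patient. Where it is not the worst, the tabulated worst grade does not change. In the transition tables the distortion can go in either direction. The size cannot be determined from the documents.

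Four stronger conclusions might be drawn, and the documents do not support them:

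- That all laboratory tables are biased towards less toxicity. This fails for transitions, as the last-value and baseline examples show.
- That only abnormal values are removed. Two different grades imply that at least one is above 0, but the SAP does not list the pairs.
- That all ten parameters matter equally in this trial. Six are in the scheduled panel.
- That dose escalation or the MTD is compromised. Under Protocol 4.1.7, DLTs are classified from adverse events after review by the investigators and the medical monitor. Nothing shows that the -1 rule enters that process or the BLRM.

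**What to change.** Amend SAP 7.8.2 in four respects:

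1. In the worst-grade and grade-transition tables, count each -1 value at the lower of its two candidate grades. The worst-grade table is then a lower bound that keeps every patient with a value.
2. Footnote, per parameter and dose, how many patients could be at the higher grade. In the transition tables, also mark where the ambiguous value is the baseline or last value, since a lower grade there does not bound the change.
3. Keep -1 in the listings.
4. State that the numeric values stay in the baseline, last-value and difference summaries and in the reference-range summaries. This also keeps the SAP in line with Protocol 7.3.4.

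The cost is some SAP wording and a small derivation change. No new data are needed. The downside is that some values will still be graded low, by one step where the two candidate grades are adjacent.
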